8.6.4. Clinical Laboratory Evaluations

All clinical laboratory evaluations will be summarized for the Safety Analysis Set for each cumulative dose group and for all groups combined. Descriptive summaries (mean, SD, median, minimum, and maximum) of absolute values and changes from baseline values will be presented for clinical laboratory values at each time point. Summaries will be performed using the standard units for each analyte. These summaries will be conducted over time using the windows specified in Section 6.2.4.

The number of patients with clinical laboratory values below, within, or above normal ranges for each time point will be tabulated (shift tables) for each clinical laboratory analyte by cumulative dose group.

The proportion of patients who have a clinically significant laboratory result will be summarized by time point for each parameter using frequencies and percentages.

Specific liver-related laboratory results will be summarized by cumulative dose groups and by time point. The specific results summarized will be $AST \geq 3 \times ULN$, $ALT \geq 3 \times ULN$, and AST or $ALT \geq 3 \times ULN$; $AST \geq 5 \times ULN$, $ALT \geq 5 \times ULN$, and AST or $ALT \geq 5 \times ULN$; and $BILI \geq 2 \times ULN$.

For clinically significant and shift summaries, the worst overall value reported will be displayed. These "worst" results will be calculated as the maximum absolute change from baseline.

In addition, laboratory measurements listing will be presented for each patient.

No statistical inference between the treatments will be performed for laboratory evaluations.

Client: Trevena, Inc.
Version #: 1.0
Version Date: 20Dec2016

Protocol/CIP #: CP130-3003

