3.1.3 Predose period

Before dosing with oliceridine, vital signs (blood pressure, heart rate, respiratory rate), oxygen saturation, and somnolence/sedation will be measured. Somnolence/sedation will be measured using the MRPSS. During the predose period, an additional, post-surgical ECG will be performed only in surgical patients. Prior medications and AEs/SAEs will be recorded.

Pain intensity will be measured using a 0-10 point numeric pain rating scale (NPRS).

Predose period procedures will occur within 30 minutes before the first oliceridine dose. If the dosing period is delayed, predose period procedures (except the additional, post-surgical ECG performed only in surgical patients) will be repeated.

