3.1.5 End of treatment phase

When the investigator documents that the last dose of oliceridine was administered and that the patient will no longer be treated with oliceridine, the treatment phase is complete and the end of treatment phase begins. A physical examination will be performed at this time.

Within 1 hour after completion of the treatment phase, vital signs, oxygen saturation, and somnolence/sedation will be measured, and concomitant medications and AEs/SAEs will be recorded.

Within 3 hours after completion of the treatment phase, blood will be collected for clinical laboratory tests. Concomitant medications and AEs/SAEs will be recorded.

Trevena, Inc.

Protocol CP130-3003

Version 5.0

14 Sep 2016

Patients will be observed for at least three hours after the last dose of oliceridine; however, medically-required transfer of an ED patient to another facility takes precedence over study procedures.

The Subjective Opioid Withdrawal Scale (SOWS) will be administered to detect symptoms of opioid withdrawal. If the patient is discharged or transferred before the time when the SOWS is to be performed, it will be performed one day after completion of the treatment phase and returned to the site by mail or in person.

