3.6 Study Procedures

Study procedures are outlined in the Schedule of Events ([Table 2](#)); selected procedures are described thereafter.

Forma

Trevena, Inc.

Protocol CP130-3003

Version 5.0

14 Sep 2016

Table 2: Schedule of Events

Procedures	Screening phase ¹ (≤ 14 days before first dose of oliceridine)	Baseline phase ¹ (Day 1)	Treatment phase (up to 14 days)		End-of-treatment phase ²				Follow-up phase ³ (Between 2 days and 3 days after completion of treatment phase)
			Predose (Day 1)	T0 to last dose of oliceridine ⁴	End-of-treatment documentation ²	Within 1 hour after completion of treatment phase ²	Within 3 hours after completion of treatment phase ²	One day after completion of treatment phase	
Informed consent ⁵	X								
Demographics	X								
Medical history	X	X							
Eligibility criteria	X	X							
ASA physical status classification ⁶	X	X							
ESI ⁷	X								
Physical examination ²	X	X			X				
Clinical laboratories ⁸	X	X					X		
Blood sample for future CYP2D6 genotyping				X					
Urine or serum pregnancy test ⁹	X	X							
Urine or serum toxicology screen ¹⁰	X								
Weight	X	X							
Height ¹¹	X								
ECG	X	X	X ¹²	X ¹³					
PK sampling ¹⁴				X					
PCA patient training ¹⁵	X	X	X	X					
Oliceridine dosing				X					
NPRS ¹⁶		X	X	X		X			
Vital signs ¹⁷	X	X	X	X		X			
MRPSS ¹⁸			X	X		X			
SOWS ¹⁹								X	
Oxygen saturation ²⁰			←-----X-----→						
Prior, concomitant medications ²¹	←-----X-----→		←-----X-----→						
AE/SAE reporting ²²	←-----X-----→								

Confidential

Page 37 of 67

Trevena, Inc.

Protocol CP130-3003

Version 5.0

14 Sep 2016

Abbreviations: AE = adverse event; ASA = American Society of Anesthesiologists; CYP2D6 = cytochrome P450 2D6; ECG = electrocardiogram; ESI = Emergency Severity Index; MRPSS = Moline-Roberts Pharmacologic Sedation Scale; NPRS = Numeric Pain Rating Scale; PCA = patient-controlled analgesia device; PK = pharmacokinetic; SAE = serious adverse event; SOWS = Subjective Opiate Withdrawal Scale; T0 = time of first oliceridine dose.

1. When screening and baseline procedures are anticipated to occur within 48 hours of each other, they may be executed as a single procedure, unless the clinical condition of the patient has significantly changed since screening.

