3.6.1 Screening and Baseline Procedures

- When screening and baseline procedures are anticipated to occur within 48 hours of each other, they may be executed as a single procedure, unless the clinical condition of the patient has significantly changed since screening.
- For this study, AE reporting begins from time of informed consent.
- Height without shoes will be measured or obtained by patient attestation and recorded in inches. Weight without shoes will be measured and recorded in pounds.
- Urine or serum pregnancy test will be performed on female patients of childbearing potential only. Tests obtained before informed consent may be used as study data if obtained within 24 hours before the first dose of oliceridine or obtained during the current ED visit.
- Standard, 12-lead ECG will be captured using local equipment. Tests obtained before informed consent may be used as study data if obtained within 14 days before the first dose of oliceridine or obtained during the current ED visit.
- PCA patient training is required before PCA use. If PCA is planned, training will occur during the screening and baseline phases; if PCA is started during the treatment phase, training will occur before PCA use. Training is repeated according to patient need.
- American Society of Anesthesiologists (ASA) Physical Status Classification System score (if a surgical or medical patient); if an ED patient, Emergency Severity Index (ESI) triage score (if an ED patient) (see Sections 9.3 and 9.4).
- If an ED patient, urine or serum toxicology screen. Test results obtained before informed consent may be used as study data if obtained during the current ED visit.
- Clinical laboratories include blood chemistry and hematology. These will be obtained using local laboratories and local laboratory range values. Tests obtained before informed consent may be used as study data if obtained within 14 days before the first dose of oliceridine or obtained during the current ED visit.
- Physical examinations will include examination of general appearance, skin, neck (including thyroid), eyes, ears, nose, throat, heart, lungs, abdomen, lymph nodes, extremities, and nervous system.

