6.3.3 Clinical Laboratory Evaluations

Baseline values are defined as the last measurements taken before the first dose of oliceridine. Change from baseline will be defined as the post baseline value minus the baseline value.

The investigator will exercise his or her medical and scientific judgment in deciding whether an abnormal laboratory finding or other abnormal assessment is clinically significant.

Liver chemistry thresholds have been designed to assure patient safety. When patients meet the hepatic transaminase threshold criteria (AST or ALT $\geq 3 \times$ upper limit of normal [ULN]), the patient should undergo close observation, including monitoring for symptoms (clinical symptoms of hepatitis or hypersensitivity, fatigue, decreased appetite, nausea, vomiting, abdominal pain, jaundice, fever, or rash) and hepatic function (AST, ALT, alkaline phosphatase, and fractionated bilirubin) at least every 48 hours, until symptoms and/or hepatic function abnormalities resolve, stabilize, or return to baseline values. The following thresholds will be derived and presented for hepatic chemistry:

- AST $\geq 3 \times$ ULN
- ALT $\geq 3 \times$ ULN
- AST or ALT $\geq 3 \times$ ULN
- AST $\geq 5 \times$ ULN
- ALT $\geq 5 \times$ ULN
- AST or ALT $\geq 5 \times$ ULN
- BILI $\geq 2 \times$ ULN

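### Laboratory changes in surgical patients probably mix operation with drug and are pooled across settings, and the hepatic 'on treatment' counts ignore baseline

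*SAP*

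**What the plan says.** **Timing.** In Protocol Table 2 (Section 3.6) the row for "Clinical laboratories" is marked at screening, at the baseline phase (Day 1) and within 3 hours after the treatment phase ends. The predose and dosing columns are empty. Section 3.1.5 agrees on the last sample: "Within 3 hours after completion of the treatment phase, blood will be collected for clinical laboratory tests". Section 3.1.3 lists the predose work: "Before dosing with oliceridine, vital signs (blood pressure, heart rate, respiratory rate), oxygen saturation, and somnolence/sedation will be measured". It adds pain intensity and, for one group only, an ECG: "During the predose period, an additional, post-surgical ECG will be performed only in surgical patients".

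**Age of the sample.** Screening and baseline may be one procedure if expected within 48 hours of each other, "unless the clinical condition of the patient has significantly changed since screening". For laboratories, Section 3.6.1 adds: "Tests obtained before informed consent may be used as study data if obtained within 14 days before the first dose of oliceridine".

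**Analysis.** SAP 6.2.1 takes as baseline the last non-missing value before the first dose, including unscheduled and repeat values. SAP 8.6.4 summarises laboratories by cumulative dose group and overall: "changes from baseline values will be presented for clinical laboratory values at each time point". The worst value, used in the shift and clinically-significant tables, is the one with the largest absolute change from baseline. SAP 7.7 lists initial setting among the safety subgroups.

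**Hepatic rows.** SAP 6.3.3 says "The following thresholds will be derived and presented for hepatic chemistry" and lists AST, ALT and either enzyme at 3 and 5 times the upper limit of normal (ULN), and bilirubin at 2 times. Mock Table 14.3.4.1, titled as findings on treatment, requires only a non-missing value in the window.

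**A conflict.** SAP 4.1 includes clinical laboratory tests in the blood drawn during dosing. The matching sentence in Protocol 3.1.4 does not, and neither schedule marks such a sample.

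**The concern.** The protocol re-measures the ECG after surgery and before dosing, but not the laboratories. If the last laboratory value before the first dose was taken before the operation, the end-of-treatment comparison spans blood loss, fluids, anaesthesia and tissue injury as well as oliceridine. There is no control arm to separate them.

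Laboratory assessment is a named part of the safety and tolerability endpoint (Protocol 1.3.1). A pooled change table could show a shift that comes from surgery, or hide a drug effect in the opposite direction. Dose group is the dose actually received under as-needed dosing (SAP 4.2). If the proportion of surgical patients differs between dose groups, an operative effect can therefore look like a dose gradient or mask one.

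The hepatic table has a separate problem. A patient who was at or above a threshold before the first dose, and did not change, is counted as an on-treatment finding.

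**Working it through.** **1. Is the laboratory baseline pre-operative?** The predose ECG is described as additional and post-surgical. It adds to the screening and baseline ECGs, which stand in the same Table 2 columns as the screening and baseline laboratories. The schedule therefore treats those columns as normally before the operation. No sentence says so for laboratories, so this is an inference, though a strong one.

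**2. Which baseline enters the analysis?** Under SAP 6.2.1 an unscheduled post-operative, pre-dose sample would replace the earlier one. Surgical patients can thus have two kinds of baseline, and no table or listing distinguishes them. Where a patient has more than one post-dose value, the baseline also decides which is displayed as worst.

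**3. Size of the pooled shift.** The plan gives no figure to reproduce. For illustration:

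pooled mean change = D + π × S

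Here D is the drug effect, π the share of all patients who are surgical with a pre-operative baseline, and S the operative shift between that baseline and the end-of-treatment sample. The documents give neither π nor S, so both are assumed. With D = 0:

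| π | S = 0.25 SD | S = 0.5 SD | S = 1.0 SD |
|---|---|---|---|
| 0 | 0 | 0 | 0 |
| 0.25 | 0.06 | 0.13 | 0.25 |
| 0.50 | 0.13 | 0.25 | 0.50 |
| 0.75 | 0.19 | 0.38 | 0.75 |

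None of this would be due to oliceridine.

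**4. Dose gradient.** The spurious difference between two dose groups is (π₂ − π₁) × S. With assumed shares of 0.25 and 0.75 and S = 0.5 SD, it is 0.5 × 0.5 = 0.25 SD.

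**5. Is the setting shown elsewhere?** The mock displays repeat the exposure table (14.3.1.9) and the overall TEAE table (14.3.2.1.7) by initial setting. None of the laboratory tables (14.3.3.1, 14.3.3.2, 14.3.3.1.1, 14.3.3.2.1, 14.3.3.1.2, 14.3.3.2.2, 14.3.4.1) is repeated.

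**6. Hepatic count.** Take a patient with AST 4 × ULN and normal ALT at baseline, and the same after dosing.
- Exclusion 11 joins its AST and ALT conditions (each at 1.5 × ULN) with AND. The ALT part is not met, so it does not exclude the patient.
- Exclusion 13 applies only if the value is known or obtained at screening and judged clinically significant.
- If enrolled, the patient is counted under AST ≥ 3 × ULN and under AST or ALT ≥ 3 × ULN, with a change of 4 − 4 = 0.

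The same holds for a patient with normal screening values whose AST rises after the operation and is recorded before the first dose.

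**The case against.** **The primary measure is adverse events, not laboratory means.** Clinically significant abnormalities become AEs (Protocol 4.1.3) with a causality rating (4.1.4.2), and overall TEAEs are shown by setting. The laboratory tables are descriptive and claim no attribution. This is fair and limits the damage. However, signs anticipated for a surgical or medical patient are not recorded as AEs unless worse than expected (4.1.1), so the AE tables cannot fully stand in for the laboratory tables.

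**Baselines up to two weeks old.** A reader might infer from the 14-day rule that the baseline is routinely that old. The documents do not support this. Table 2 schedules a Day 1 baseline sample, merging with screening is limited to 48 hours, and the 14-day rule concerns which pre-consent tests may be used. The confounding does not depend on the sample's age.

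**An operation might count as a significant clinical change** and so force a new baseline sample. That is possible on the wording, but it would have made the extra ECG unnecessary.

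**SAP 4.1 implies samples during dosing.** Such samples would still follow the operation, so they do not help.

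**High transaminases would rarely get in.** Protocol 4.1.3 treats 3 × ULN as a threshold for close observation, so many such values would be judged clinically significant at screening. This stands: the number affected is probably small. The shift tables show baseline status only as low, normal or high, so they cannot identify who was already above a multiple of ULN.

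**Medical and ED patients are not clean either.** Pancreatitis, burns, trauma and sickle-cell episodes also move laboratory values. This stands. Splitting by setting makes the confounding visible but does not remove it.

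**Conclusion.** The plan should be changed on presentation and counting. In surgical patients with a pre-operative baseline, the change, shift and worst-value laboratory results cannot separate oliceridine from the operation, and the tables pool these patients with the others. The illustrated pooled shift of 0.06–0.75 SD rests wholly on assumed shares (25–75%) and shifts (0.25–1.0 SD), and is nil if no such patients exist. The missing predose sample, the pooling and the absence of a baseline condition in Table 14.3.4.1 are plain in the text. The pre-operative timing is inferred.

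A reader might infer that the laboratory data cannot show oliceridine's laboratory safety at all. That goes too far. This mechanism touches surgical patients only. Absolute values and ULN multiples do not use the baseline: they can still show how often marked elevations occur, although not their cause. Nor would a post-operative baseline settle attribution, because in a single-arm study the continuing post-operative course would remain.

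**What to change.** - **By setting.** In SAP 8.6.4, repeat the laboratory change, shift, clinically-significant and hepatic tables listed in step 5 by initial setting (surgical, medical, ED), as SAP 7.7 already implies.
- **Hepatic table.** In Table 14.3.4.1, count a threshold as emergent only when the baseline was below it, and put patients already at or above it on a separate row. For the combined AST or ALT rows, state whether both enzymes must start below.
- **Baseline flag.** Where the operation time is available, flag each surgical baseline as before or after surgery. The documents do not show that this time is collected. The listed times of laboratory samples, post-surgical ECGs and prior medications may help; otherwise it needs a site query.
- **Wording.** Describe laboratory changes in surgical patients as not attributable to drug alone, without declaring medical or ED patients free of confounding.
- **Consistency.** Reconcile SAP 4.1 with Protocol 3.1.4 and both schedules on laboratory blood during dosing.

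**Cost.** The tables by setting and the hepatic rows use data already collected and need no extra blood sample. There are more tables and fewer patients in each. For an event not seen, the one-sided 95% upper bound is 1 − 0.05^(1/n): 0.30% for 1000 patients, and 0.60%, 1.19% or 2.95% for a setting with 500, 250 or 100. The documents do not give the split, so these sizes are assumptions. The pooled tables remain alongside.

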3.6.2.6 Clinical Laboratories

Clinical laboratories include blood chemistry and hematology obtained using local laboratories and local laboratory range values.

Chemistry includes: Albumin, total bilirubin, total protein, calcium, alkaline phosphatase, alanine aminotransferase (ALT), aspartate aminotransferase (AST), blood urea nitrogen (BUN), creatinine, glucose, sodium, potassium, chloride, bicarbonate, lactate dehydrogenase, and uric acid.

Hematology includes: hemoglobin, hematocrit, red blood cell (RBC) count, RBC indices, mean corpuscular hemoglobin (MCH), mean corpuscular hemoglobin concentration (MCHC), platelet count (or estimate), and white blood cell (WBC) count including differential.

Urine or serum toxicology includes any standard of care analytes at the institution where the study is being conducted.

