Mean (SD)		xx.x (x.xx)	xx.x (x.xx)	xx.x (x.xx)	xx.x (x.xx)	xx.x (x.xx)	xx.x (x.xx)	
Median		xx.x	xx.x	xx.x	xx.x	xx.x	xx.x	
Min, Max		xx, xx	xx, xx	xx, xx	xx, xx	xx, xx	xx, xx	
n	Observed	xxx	xxx	xxx	xxx	xxx	xxx	
Mean (SD)		xx.x (x.xx)	xx.x (x.xx)	xx.x (x.xx)	xx.x (x.xx)	xx.x (x.xx)	xx.x (x.xx)	
Median		xx.x	xx.x	xx.x	xx.x	xx.x	xx.x	
Min, Max		xx, xx	xx, xx	xx, xx	xx, xx	xx, xx	xx, xx	
n	Change	xxx	xxx	xxx	xxx	xxx	xxx	
Mean (SD)		xx.x (x.xx)	xx.x (x.xx)	xx.x (x.xx)	xx.x (x.xx)	xx.x (x.xx)	xx.x (x.xx)	
Median		xx.x	xx.x	xx.x	xx.x	xx.x	xx.x	
Min, Max		xx, xx	xx, xx	xx, xx	xx, xx	xx, xx	xx, xx	
...								

Note: Percentages are based on the number of patients in each cumulative dose group.

[a] See section 6.2.3 of the SAP for windowed time point intervals.

[b] Baseline is the last non-missing value prior to the patient receiving the first dose of oliceridine.

Parameter (unit) Windowed Time Point[a]	Baseline/ Observed/ Change from Baseline	Oliceridine <= 4 mg N=XXX	Oliceridine >4 to 8 mg N=XXX	Oliceridine >8 to 16 mg N=XXX	Oliceridine >16 to 36 mg N=XXX	Oliceridine >36 mg N=XXX	All Treated Patients N=XXX
<hr/>							

[c] Only patients with both a baseline value and a windowed time point value are summarized at a given windowed time point.

Programmer's Note: Repeat Parameter (unit) in each page if it wraps on to multiple pages.

Use the same template as for Table 14.3.3.1 for the following tables:

Table 14.3.3.2
Summary of Clinical Laboratory Results: Chemistry
(Safety Analysis Set)

Table 14.3.3.1.1
Clinical Laboratory Hematology Results for Shifts from Baseline
(Safety Analysis Set)

Parameter (unit)	Windowed Time Point[a]	Cumulative dose group	Baseline [b]	Post Baseline				Total n (%)	Missing
				Low n (%)	Normal n (%)	High n (%)			
<Parameter 1 (unit)> Oliceridine <= 4 mg (N=XXX)									
Worst Post Baseline				Low	xxx (xxx.x)	xxx (xxx.x)	xxx (xxx.x)	xxx (xxx.x)	xxx
				Normal	xxx (xxx.x)	xxx (xxx.x)	xxx (xxx.x)	xxx (xxx.x)	xxx
				High	xxx (xxx.x)	xxx (xxx.x)	xxx (xxx.x)	xxx (xxx.x)	xxx
				Total	xxx (xxx.x)	xxx (xxx.x)	xxx (xxx.x)	xxx (xxx.x)	xxx
				Missing	xxx	xxx	xxx	xxx	xxx
<T30 Minutes>				Low	xxx (xxx.x)	xxx (xxx.x)	xxx (xxx.x)	xxx (xxx.x)	xxx
				Normal	xxx (xxx.x)	xxx (xxx.x)	xxx (xxx.x)	xxx (xxx.x)	xxx
				High	xxx (xxx.x)	xxx (xxx.x)	xxx (xxx.x)	xxx (xxx.x)	xxx
				Total	xxx (xxx.x)	xxx (xxx.x)	xxx (xxx.x)	xxx (xxx.x)	xxx
				Missing	xxx	xxx	xxx	xxx	xxx
...									
<Time Point n>				Low	xxx (xxx.x)	xxx (xxx.x)	xxx (xxx.x)	xxx (xxx.x)	xxx

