				Normal	xxx (xxx.x)	xxx (xxx.x)	xxx (xxx.x)	xxx (xxx.x)	xxx
				High	xxx (xxx.x)	xxx (xxx.x)	xxx (xxx.x)	xxx (xxx.x)	xxx
				Total	xxx (xxx.x)	xxx (xxx.x)	xxx (xxx.x)	xxx (xxx.x)	xxx
				Missing	xxx	xxx	xxx	xxx	xxx

Note: Low = below normal reference range; Normal = within normal reference range; High = above normal reference range.
Percentages are based on the number of patients with a non-missing baseline and post-baseline windowed time point value within each windowed time point, parameter and cumulative dose group.

Worst post-baseline is calculated as the most extreme absolute change from baseline value.

[a] See section 6.2.3 of the SAP for windowed time point intervals.

[b] Baseline is the last non-missing value prior to the patient receiving the first dose of oliceridine.

Trevena, Inc.
Protocol CP130-3003

CONFIDENTIAL
Page x of y

Use the same template as for Table 14.3.4.1.3 for the following tables:

Table 14.3.3.2.1
Clinical Laboratory Chemistry Results for Shifts from Baseline
(Safety Analysis Set)

Table 14.3.3.1.2
Clinically Significant Clinical Laboratory Hematology Results
(Safety Analysis Set)

Parameter (unit)	Oliceridine <= 4 mg N=XXX n (%)	Oliceridine >4 to 8 mg N=XXX n (%)	Oliceridine >8 to 16 mg N=XXX n (%)	Oliceridine >16 to 36 mg N=XXX n (%)	Oliceridine >36 mg N=XXX n (%)	All Treated Patients N=XXX n (%)
Windowed Time Point [a]						
Interpretation						
Patients with at Least 1 Clinically Significant Hematology Result	xxx (xxx.x)	xxx (xxx.x)	xxx (xxx.x)	xxx (xxx.x)	xxx (xxx.x)	xxx (xxx.x)
<Parameter 1 (unit)>						
Baseline [b]	xxx (xxx.x)	xxx (xxx.x)	xxx (xxx.x)	xxx (xxx.x)	xxx (xxx.x)	xxx (xxx.x)
Normal	xxx (xxx.x)	xxx (xxx.x)	xxx (xxx.x)	xxx (xxx.x)	xxx (xxx.x)	xxx (xxx.x)
Abnormal, NCS	xxx (xxx.x)	xxx (xxx.x)	xxx (xxx.x)	xxx (xxx.x)	xxx (xxx.x)	xxx (xxx.x)
Abnormal, CSig	xxx (xxx.x)	xxx (xxx.x)	xxx (xxx.x)	xxx (xxx.x)	xxx (xxx.x)	xxx (xxx.x)
Missing	xxx (xxx.x)	xxx (xxx.x)	xxx (xxx.x)	xxx (xxx.x)	xxx (xxx.x)	xxx (xxx.x)
Worst Post-Baseline Value	xxx (xxx.x)	xxx (xxx.x)	xxx (xxx.x)	xxx (xxx.x)	xxx (xxx.x)	xxx (xxx.x)
Normal	xxx (xxx.x)	xxx (xxx.x)	xxx (xxx.x)	xxx (xxx.x)	xxx (xxx.x)	xxx (xxx.x)
Abnormal, NCS	xxx (xxx.x)	xxx (xxx.x)	xxx (xxx.x)	xxx (xxx.x)	xxx (xxx.x)	xxx (xxx.x)
Abnormal, CSig	xxx (xxx.x)	xxx (xxx.x)	xxx (xxx.x)	xxx (xxx.x)	xxx (xxx.x)	xxx (xxx.x)
Missing	xxx (xxx.x)	xxx (xxx.x)	xxx (xxx.x)	xxx (xxx.x)	xxx (xxx.x)	xxx (xxx.x)

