<T30 Minutes>	xxx (xxx.x)	xxx (xxx.x)	xxx (xxx.x)	xxx (xxx.x)	xxx (xxx.x)	xxx (xxx.x)
Normal	xxx (xxx.x)	xxx (xxx.x)	xxx (xxx.x)	xxx (xxx.x)	xxx (xxx.x)	xxx (xxx.x)
Abnormal, NCS	xxx (xxx.x)	xxx (xxx.x)	xxx (xxx.x)	xxx (xxx.x)	xxx (xxx.x)	xxx (xxx.x)
Abnormal, CSig	xxx (xxx.x)	xxx (xxx.x)	xxx (xxx.x)	xxx (xxx.x)	xxx (xxx.x)	xxx (xxx.x)
Missing	xxx (xxx.x)	xxx (xxx.x)	xxx (xxx.x)	xxx (xxx.x)	xxx (xxx.x)	xxx (xxx.x)
...						

Note: NCS = Not clinically significant; CSig = Clinically significant.

Clinical significance is based on the investigator interpretation as recorded.

Percentages are based on the number of patients with a non-missing baseline and post-baseline windowed time point value within each windowed time point, parameter and cumulative dose group.

Worst post-baseline is calculated as the most extreme absolute change from baseline value.

Trevena, Inc.
Protocol CP130-3003

CONFIDENTIAL
Page x of y

- [a] See section 6.2.3 of the SAP for windowed time point intervals.
- [b] Baseline is the last non-missing value prior to the patient receiving the first dose of oliceridine.

Programmer's Note: Continue with all parameters and all windowed time points even if all counts are 0.

Use the same template as for Table 14.3.3.1.2 for the following tables:

Table 14.3.3.2.2
Clinically Significant Clinical Laboratory Chemistry Results
(Safety Analysis Set)

Table 14.3.4.1
Select Hepatic Laboratory Findings on Treatment
(Safety Analysis Set)

Windowed Time Point [a] Test Result	Oliceridine <= 4 mg N=XXX n (%)	Oliceridine >4 to 8 mg N=XXX n (%)	Oliceridine >8 to 16 mg N=XXX n (%)	Oliceridine >16 to 36 mg N=XXX n (%)	Oliceridine >36 mg N=XXX n (%)	All Treated Patients N=XXX n (%)
Patients with at Least 1 Hepatic Laboratory Finding						
AST >=3 X ULN	xxx (xxx.x)	xxx (xxx.x)	xxx (xxx.x)	xxx (xxx.x)	xxx (xxx.x)	xxx (xxx.x)
ALT >=3 X ULN	xxx (xxx.x)	xxx (xxx.x)	xxx (xxx.x)	xxx (xxx.x)	xxx (xxx.x)	xxx (xxx.x)
AST or ALT >=3 X ULN	xxx (xxx.x)	xxx (xxx.x)	xxx (xxx.x)	xxx (xxx.x)	xxx (xxx.x)	xxx (xxx.x)
AST >=5 X ULN	xxx (xxx.x)	xxx (xxx.x)	xxx (xxx.x)	xxx (xxx.x)	xxx (xxx.x)	xxx (xxx.x)
ALT >=5 X ULN	xxx (xxx.x)	xxx (xxx.x)	xxx (xxx.x)	xxx (xxx.x)	xxx (xxx.x)	xxx (xxx.x)
AST or ALT >=5 X ULN	xxx (xxx.x)	xxx (xxx.x)	xxx (xxx.x)	xxx (xxx.x)	xxx (xxx.x)	xxx (xxx.x)
BILI >=2 X ULN	xxx (xxx.x)	xxx (xxx.x)	xxx (xxx.x)	xxx (xxx.x)	xxx (xxx.x)	xxx (xxx.x)
<T30 Minutes>						
AST >=3 X ULN	xxx (xxx.x)	xxx (xxx.x)	xxx (xxx.x)	xxx (xxx.x)	xxx (xxx.x)	xxx (xxx.x)

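### The worst laboratory row is selected by size of change but classified by range or rating, so with repeat draws it can read Normal over an abnormal value

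*SAP*

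**What the plan says.** SAP 8.6.4 (Clinical Laboratory Evaluations) says that in the clinically significant and shift summaries "the worst overall value reported will be displayed", and that the worst "results will be calculated as the maximum absolute change from baseline". The footnotes to mock Tables 14.3.3.1.1 (hematology shifts) and 14.3.3.1.2 (clinically significant hematology) repeat the rule: "Worst post-baseline is calculated as the most extreme absolute change from baseline value".

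The shift table has a "Worst Post Baseline" block that sorts the selected record into Low, Normal or High by reference range. The clinically significant table sorts it into Normal, Abnormal NCS or Abnormal CSig by the investigator's recorded interpretation.

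The chemistry tables reuse these shells. For clinically significant chemistry the instruction is "Use the same template as for Table 14.3.3.1.2 for the following tables". For chemistry shifts it is "Use the same template as for Table 14.3.4.1.3 for the following tables". That number is not in the table list; from its position it must mean 14.3.3.1.1.

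On timing, Protocol 3.1.5 has one post-treatment draw: "Within 3 hours after completion of the treatment phase, blood will be collected for clinical laboratory tests". The schedules of events in both documents also show only that one.

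**The concern.** Selection and classification use different scales. The size of a change ignores its direction, whether the value lies in range, and how the investigator rated it. A patient with one abnormal and one in-range post-baseline value is shown as Normal whenever the in-range value lies further from baseline. From an abnormal baseline, the rule can even report a recovery as the worst value.

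Safety is the primary objective, and these tables are its per-parameter summary of laboratory abnormalities. A reader will take a worst row reading Normal to mean that no abnormal value occurred for that analyte. Under this rule that inference is unsafe for anyone with more than one post-baseline draw.

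**Working it through.** The plan gives no figure to reproduce. The check applies the SAP rule directly: select the value x with the largest |x − baseline|, then classify that x.

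**1. Can the row contradict its label?** Assumed potassium range 3.5–5.0, baseline 3.6, two later draws:

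| Draw | Value | Change | Class |
|---|---|---|---|
| 1 | 2.9 | −0.7 | Low |
| 2 | 4.7 | +1.1 | Normal |

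Since 1.1 > 0.7, the rule selects 4.7 and the row reads Normal. From a raised baseline (assumed range 70–100, baseline 180, then 200 and 95) the changes are +20 and −85; the rule selects 95, again Normal. Reading the rule as the largest signed change does not rescue it. With assumed range 135–145, baseline 140, then 130 and 141, the largest signed change is +1, so 141 is selected and the Low value is lost. With one draw there is nothing to choose between, and no error.

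**2. When could there be more than one draw?** Protocol 4.3.2 calls for urgent laboratory assessment after a QTcF stop. It does not say whether this is separate from the end-of-treatment draw. Protocol 4.1.3 calls for hepatic tests at least every 48 hours once AST or ALT reaches 3 × ULN. SAP 4.1 also lists clinical laboratory tests among the blood collected during dosing, which the schedule does not show. None of these gives a number of patients.

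**3. How often, as an illustration?** The potassium inputs are assumptions, not trial data: mean 4.1, between-patient SD 0.3, within-patient SD 0.3 or 0.4, range 3.5–5.0, baseline in range, independent draws around each patient's own mean. Simulation with 2,000,000 patients per setting (results for SD 0.3 / 0.4):

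| | 1 draw | 2 draws | 3 draws |
|---|---|---|---|
| Wrongly shown in range, % of all patients | 0 / 0 | 1.78 / 3.13 | 3.67 / 6.32 |
| Same, % of those with any out-of-range value | – | 12.9 / 13.0 | 19.4 / 19.3 |
| Median distance of masked value beyond the limit | – | 0.079 / 0.106 | 0.088 / 0.120 |
| Masked value within 0.2 of the limit, % | – | 85.6 / 74.7 | 82.3 / 70.5 |
| Masked with a value <3.0 or >5.5, % of all patients | – | 0.005 / 0.054 | 0.015 / 0.153 |

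If 1–10% of the planned 1000 patients (10 to 100) had repeat draws, also an assumption, the counts for one such analyte would be:

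- two draws: 10 × 0.0178 = 0.18 to 100 × 0.0313 = 3.1 patients;
- three draws: 10 × 0.0367 = 0.37 to 100 × 0.0632 = 6.3 patients.

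**4. How large a liver value can be hidden?** Work in ULN units with a normal baseline b ≤ 1 and an elevated value x > 1. An in-range value above b differs from b by at most 1 − b, which is less than x − b, so it cannot displace x. An in-range value below b differs by at most b, so it displaces x only if x − b < b, that is x < 2b. This gives x < 1.6 at b = 0.8 and x < 2.0 at b = 1.0; for b < 0.5 nothing elevated is masked. From a normal baseline, no AST, ALT or bilirubin value at or above 2 × ULN can be hidden.

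**The case against.** The strongest reply is that the row rarely matters.

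- **Reach.** One draw is scheduled, and one draw gives no error. Hepatic follow-up starts at 3 × ULN, and by step 4 that triggering value cannot be masked from a normal baseline. This stands. What remains there is milder companion values and patients whose baseline was already raised. The SAP 4.1 mention of laboratory draws during dosing points the other way, since it would widen the reach.
- **Other displays.** Time-point rows show the abnormal value if the draws fall in different windows. End-of-treatment values are summarised separately, and Table 14.3.4.1 counts the hepatic thresholds. Clinically significant findings that meet the AE definition are recorded and tabulated as AEs. The clinically significant tables open with a count of patients having at least one such result, and listings show every value. All this limits the harm, but none of it corrects the row. SAP 6.2.4 keeps one record per window, the one nearest the midpoint; the opening count is not per parameter; the shift table has no equivalent; and out-of-range values not rated clinically significant do not reach the AE tables by this route.
- **Magnitude.** The figures are assumed. With both SDs at 0.2, two-draw masking falls to 0.4% of patients. This stands, and is why they serve only as illustration.
- **Disclosure.** The footnotes state the definition, so relabelling the shift row as largest absolute change would make label and content agree with no new lines. That would be honest, but it would not deliver the worst value that SAP 8.6.4 promises.

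**Conclusion.** The concern holds and is minor. The SAP states a rule that, with two or more post-baseline values, can print Normal in a worst row over a Low, High or clinically significant result. The effect is zero for patients with only the scheduled draw. For an analyte like the assumed potassium, it is a few percent of those with repeat draws: about 0.2–3 patients (two draws) or 0.4–6 (three) if 1–10% of 1000 had repeats. Most masked values would be just outside the range. These figures rest on the assumed distribution, a normal baseline and the assumed repeat rate; raised baselines are not covered by the simulation. The documents do not give the number of patients with repeat draws. No test or decision depends on the row.

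**What to change.** - **Shift tables:** replace the single worst block with a lowest-value block and a highest-value block, each classified against the reference range.
- **Clinically significant tables:** use the most severe investigator rating (CSig, then NCS, then Normal) across all post-baseline records, including unscheduled ones.
- **Text:** change the sentence in SAP 8.6.4 and the two table footnotes to match. Correct the template reference for Table 14.3.3.2.1 in the same edit; that is clerical and adds no weight to the point.

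**Cost.** The shift tables gain one five-line block (Low, Normal, High, Total, Missing) per parameter and dose group. Protocol 3.6.2.6 names 16 chemistry analytes (the list starting "Chemistry includes: Albumin, total bilirubin, total protein, calcium, alkaline phosphatase"), giving 16 × 5 groups × 5 lines = 400 lines, or 16 × 6 × 5 = 480 with All Treated Patients. The seven individually named hematology tests add 7 × 5 × 5 = 175, or 7 × 6 × 5 = 210, before indices and differential. The clinically significant tables gain no lines. Programming must follow; no new data are needed.
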